Randomized Study Of Novel Enuresis Alarm (GoGoband®)Vs Standard Bedwetting Alarm

Protocol Number
2000031281

NCT05214131

Protocol Version
February 20, 2024
Version #6

IDE Number:

IDE Holder:

PRINCIPAL INVESTIGATOR:

[name]., Ph.D.
Department of Urology
[contact]
Email Address: [contact]

Confidentiality Statement:

2000031281

February 20, 2024

REVISION HISTORY:

Include the IRB approved protocol version number and date for each revision of the protocol. All version history should remain in the table and never be deleted. The oldest IRB approved version of the protocol should be listed on the top row. The most recent IRB approved version should be listed on the bottom row.

Revision #	Version Date
1	Sept 1 2021
2	Sept 9 2021
3	November 18, 2021
4	December 28, 2021
5	Jan 15 2022
6	February 20, 2024

2000031281

February 20, 2024

Synopsis

Primary Objective
 
Identify the dry night rate in patients using the GoGoband® nocturnal enuresis device vs a standard Pflaunger bedwetting alarm.

Secondary Objective (if applicable)
 
to ascertain if familial incidence of nocturnal enuresis has an effect on outcomes

Study Duration: total 3 years, 2 years active with 1 year for analysis

Study Design
 
Include a high-level description of the study design.
 
This is a prospective randomized comparison of GoGoband® vs standard nocturnal enuresis alarm

Number of Study Sites
 
Study sites will include all clinic sites where patients are seen in the Yale New Haven Health System
 
Yale New Haven Children’s Hospital clinic WP2 Yale New Haven Children’s Hospital Longwharf Clinic Yale New Haven Children’s Hospital Trumbull clinic Yale New Haven Children’s Hospital Norwalk clinic Yale New Haven Children’s Hospital Greenwich Clinic

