6.1.2 Device Administration and Schedule

SNEA: Device Will be provided to the patient

1. Instruction will be provided on how to set up the device and use it
2. The device will be worn consecutively for 3 months.
3. The alarm use will be terminated if they have been dry for 3 months consecutively.

GoGoband®: Device Will be provided to the patient

1. Instruction will be provided on how to set up the device and use it
2. The device will be worn consecutively for 3 months
3. The device will follow the built in algorithm in the device to decide when to begin the weaning process.
4. The weaning process will occur automatically until there no more nights in which the system will sound impending urination alarms

Non-compliant patients will be removed from the study. Alarms will not be requested back from the participants.

Reasons for noncompliance will be the following

1. Not taking medication
2. Not using device
3. Not filling in and submitting biweekly logs.

If a bedwetting alarm breaks or is nonfunctional the device will be replaced, and the study will proceed from the last active day

Method of Assignment/Randomization (if applicable)

2000031281

February 20, 2024

Randomization will be accomplished by having 100 envelopes with 50 SNEA and 50 GoGoband® choices. The envelopes will be distributed to the sites and pulled randomly at each site.

Age matching:

After 50% enrollment in any group the average age and standard deviation of the group will be calculated and an effort to adjust enrollment so groups are age matched will be made.

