3.4.2 Sample Size Considerations

A power calculation was performed using

<http://powerandsamplesize.com/Calculators/Compare-2-Proportions/2-Sample-1-Sided>

A 2 proportion 1 sided power analysis was performed A proportion of 0.5 was used for the SNEA and an expected outcome of 0.8 for the GoGoband® the sampling ratio is 1, the power was set to 0.8 and type 1 error rate of 5%. This gives a sample size of 29 participants.

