3.4.3 Planned Analysis

3.4.3.1 Primary Analyses

Outcomes will be evaluated between the 2 groups using crosstab analysis of the data for the following data :

Wetting event: Dry or Wet

Did patient wear the device: yes or no used to measure compliance

Did patient take the medication: yes or no used to measure compliance
 Is the patient considered cured (dry 29/30 nights) : yes or no
 Is the patient partially better (improvement of 50% or more compared to pretreatment)
 Does the patient show no improvement (<50% improvement compared to Pretreatment)
 Logistic regression analysis may be performed on the incremental wet dry data vs time to achieving dryness

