3.4.3.7 Other

3.4.4 Subsets and Covariates

3.4.5 Handling of Missing Data

Patients who drop out of the study will be considered failures for purposes of the study with regards to success vs partial or failure analysis
 Dry /wet night rates will be maintained for the overall analysis of overall dry/wet ratios regardless of the patient ceases participation

4 Trial Administration

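### Children are assigned from a separate envelope stock at each clinic, but the primary crosstabs pool clinics: a minor precision and robustness gap whose size depends on an unstated envelope mix

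*Combined protocol and SAP*

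**What the plan says.** The randomisation text in section 6.1.2 reads "Randomization will be accomplished by having 100 envelopes with 50 SNEA and 50 GoGoband® choices". It continues: "The envelopes will be distributed to the sites and pulled randomly at each site". It does not say how many envelopes of each arm go to each clinic. On sites, the Synopsis says "Study sites will include all clinic sites where patients are seen in the Yale New Haven Health System" and lists five.

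For the analysis, section 3.4.3.1 says "Outcomes will be evaluated between the 2 groups using crosstab analysis of the data for the following data", and the list that follows includes cure (29 of 30 nights dry) and improvement of at least 50%. Section 3.4.1 plans the same two-group crosstab. The only model offered for the primary outcomes is optional and names no clinic term: "Logistic regression analysis may be performed on the incremental wet dry data vs time to achieving dryness". The heading "3.4.4 Subsets and Covariates" has no text under it. Section 3.4.3.4 describes the groups by age, sex and questionnaire score, not by clinic. The sample size in section 3.4.2 is a plain two-proportion calculation that does not involve clinic.

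**The concern.** When assignment is drawn within clinics, the usual expectation is that the analysis compares children within clinics. A pooled crosstab does not. What that costs depends on how the envelopes were divided, and the plan is silent on this:

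- **Balanced stock at each clinic.** The design removes clinic differences from the treatment comparison, but the pooled standard error still contains them. The test is then conservative.
- **Stock dealt at random.** Some clinics end up by chance with more GoGoband envelopes. If clinics differ in success rate, this adds noise to the difference.
- **Stock deliberately uneven.** Arm is associated with clinic by design, and a clinic difference goes straight into the treatment difference.

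At stake are some precision, protection against the third case, and a choice about clinic adjustment that is now left open until results are known.

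**Working it through.** **The plan's own figure.** Inputs from section 3.4.2: "A proportion of 0.5 was used for the SNEA and an expected outcome of 0.8 for the GoGoband", one-sided 5%, power 0.80, ratio 1. With unpooled variance, n = (1.645 + 0.842)² × (0.5×0.5 + 0.8×0.2) / 0.3² = 28.16, rounded up to 29. The stated 29 therefore reproduces as 29 per group. It makes no allowance for clinic. The work below uses 50 per arm (section 5.3.1 and the envelope count); the Synopsis gives 150 in total.

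**Assumptions, not in the documents.** Five clinics of 20 children; evenly spaced clinic success rates around 0.5; no treatment effect unless stated.

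**Stocks dealt at random.** The number of GoGoband children at a clinic is hypergeometric (100, 50, 20), with variance 20 × 0.25 × 80/99 = 4.04 and SD 2.0. The pooled difference has two parts:

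- Within clinics: (2/50) × mean of p(1−p).
- Clinic imbalance: (2/50)² × (4.04 + 4.04/4) × S = 0.0016 × 5.05 × S, where S is the sum of squared deviations of the clinic rates from their mean.

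The Mantel-Haenszel difference removes the second part but pays for uneven splits inside clinics. Its total weight averages 5 × (100 − 4.04)/20 = 23.99 instead of 25, so the within-clinic variance is multiplied by about 25/23.99 = 1.042.

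| Clinic rates | Mean p(1−p) | Within | Imbalance | Pooled | Stratified | Change |
|---|---|---|---|---|---|---|
| all 0.5 | 0.250 | 0.0100 | 0 | 0.0100 | 0.01042 | +4% |
| 0.4 to 0.6 | 0.245 | 0.0098 | 0.0002 | 0.0100 | 0.01021 | +2% |
| 0.3 to 0.7 | 0.230 | 0.0092 | 0.0008 | 0.0100 | 0.00959 | −4% |
| 0.2 to 0.8 | 0.205 | 0.0082 | 0.0018 | 0.0100 | 0.00854 | −15% |

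Simulation with 200,000 trials per row gives +4.4%, +2.3%, −3.9% and −14.7%. Stratifying breaks even when the variance of clinic rates is about 4% of 0.25, or 0.010. With evenly spaced rates that variance is twice the squared spacing, so the spacing is 0.07 and the rates run from about 0.36 to 0.64.

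The pooled one-sided type I error stays at 4.4% to 4.5% in all four rows. At rates 0.3 to 0.7 the clinic shift has SD √0.0008 = 2.8 points. It is already part of the pooled variance of 0.0100, whose standard error is 10 points.

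**Stocks balanced within clinic (10:10).** There is no clinic shift. The true variance is the Within column, but the pooled test uses about 0.25 × 2/50 = 0.0100. Simulated one-sided type I error at nominal 5%:

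- Rates 0.3 to 0.7: 3.8% pooled, 5.0% stratified.
- Rates 0.2 to 0.8: about 3% pooled, about 5% stratified.
- No clinic differences: 4.5% for both.

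**Power at 50 per arm, random dealing** (10,000 trials per scenario; clinic effects on the log-odds scale, where SD 1.0 means SNEA rates of about 20% to 80%):

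| Effect | Clinic SD | Pooled | Stratified |
|---|---|---|---|
| 0.5 vs 0.8 | 0 | 94.7% | 93.4% |
| 0.5 vs 0.8 | 0.5 | 94.7% | 94.5% |
| 0.5 vs 0.8 | 1.0 | 94.8% | 96.6% |
| 0.5 vs 0.7 | 0 | 65.6% | 64.4% |
| 0.5 vs 0.7 | 1.0 | 65.3% | 72.1% |

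**The case against.** The best defence is that one 50/50 set of 100 envelopes dealt at random to clinics amounts to unstratified complete randomisation, and a pooled comparison matches that design. The estimate is then unbiased and the standard error covers the clinic shift. At the planned effect, stratifying is neutral or slightly harmful unless clinics differ strongly. Nothing in the documents suggests that they do: the clinics belong to one health system, share eligibility rules, prior urotherapy and device instruction, and treatment takes place at home.

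Much of this stands. A reader might infer that ignoring clinic biases the result or inflates the false-positive rate; with random or balanced stocks the calculations show neither. What does not stand is the premise that random dealing is the design. Section 6.1.2 does not say so. With balanced stocks the pooled test is conservative, and with uneven stocks it is confounded. The stratified comparison is valid in all three cases, provided that both arms occur at the clinics that contribute.

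It is also fair to object that stratifying the child-level outcomes leaves the dry/wet night crosstab untouched. That table needs its own treatment and is outside this point.

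**Conclusion.** The point holds as a minor matter of precision and robustness. Assignment is drawn clinic by clinic, the primary crosstabs ignore clinic, and the missing envelope mix decides which consequence applies. With random dealing, stratifying changes the variance by between about +4% and −15% over assumed clinic rates from identical to 0.2–0.8. With balanced stocks, the pooled one-sided type I error falls to about 3.8% (rates 0.3 to 0.7) or about 3% (0.2 to 0.8). Only deliberately uneven stocks would confound clinic with treatment, and the documents do not say that they are uneven.

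A reader might take the whole imbalance component at rates 0.3 to 0.7 (0.0008 of 0.0100, or 8%) as what stratifying recovers. The net gain there is about 4%, because uneven splits within clinics cost about 4%. Nor is the cost negligible if clinics do not differ. All these sizes rest on five equal clinics and on between-clinic variation that the documents do not give.

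**What to change.** In section 3.4.3.1, compare cure and 50% improvement with a Cochran-Mantel-Haenszel test stratified by clinic, and report the stratified risk difference with its 95% CI. Fix in advance a rule for merging clinics with very few children. Include clinic in any logistic model and record it under section 3.4.4. Tabulate arm by clinic in section 3.4.3.4, and state in section 6.1.2 how many envelopes of each arm each clinic received.

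The cost is a few sentences, since the enrolling clinic should be known for every child. The statistical downside is up to about 4% more variance if clinics do not differ. That is about 1 to 2 points of power at 50 per arm (94.7% to 93.4% for 0.5 vs 0.8); at 29 per group it would be nearer 3 points (80.1% to 77.2%).

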2.1.1 Device Preclinical Experience

GoGoband® is a new biometric, artificial intelligence and machine learning powered wearable bedwetting alarm that uses Pavlovian or classical conditional training to increase the effectiveness of enuresis alarm treatment. This is accomplished with the use of heart rate data, heart rate variability (HRV) analysis and real time monitoring that combines the use of algorithms developed with machine learning to learn the individual profile of each patient. Each device consists of a photoplethysmography (PPG) heart rate sensor worn on the calf, a bedside tablet, a Bluetooth moisture sensor and a parent app. The first 7-10 wetting episodes are utilized to develop the individualized program based on HRV data to predict when an impending urination event is going to happen. Artificial intelligence in our web-based database develops hundreds of thousands of models and selects the best one to predict a urination event. As time moves along the machine learning continues to modify the signaling parameters as the child's bedwetting improves. In the weaning phase the system gradually eliminates alarming episodes in a controlled fashion and as the children continues to progress it will eliminate all alarming. Once this stage is completed and the child remains dry for a week consecutively, they are deemed cured. This process can last a few days to several months with some children using the alarm remaining dry on day one and never having another accident without the alarm going off and others remain in need of the system to continue to wake them and keep them dry.

Our most recent data indicates that we can achieve a dry night rate as high as 94% in compliant patients that use the device at least 80% of the time. these results are in stark contrast to the best reported outcomes of 70% in European SNEA studies.

In summary the GoGoband® is a new biometric, artificial intelligence and machine learning powered wearable bedwetting alarm that uses Pavlovian or classical conditional training to increase the effectiveness of enuresis alarm treatment. The non-intelligent alarms on the market today rely on a form of operant conditioning which in many cases relies on negative reinforcement i.e. waking the child up to change the bed or do their laundry.

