5.1.1 Study Date Range and Duration

Each patient will be in the study for 90 days. The study duration will be 2 years to accrue enough patients willing to participate in the study and 1 year for data analysis and publication

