5.2 Outcome Variables

5.2.1 Primary Outcome Variables

Variables:

Wetting event: Dry or Wet

Did patient wear the device: yes or no used to measure compliance

Did patient take the medication: yes or no used to measure compliance

Is the patient considered cured (dry 29/30 nights) : yes or no

Is the patient partially better (improvement of 50% or more compared to pre treatment)

Does the patient show no improvement (<50% improvement compared to Pre treatment)

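### The optional logistic regression on time to dryness does not define the event or say how children still wet at day 90, or who leave early, enter the model

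*Combined protocol and SAP*

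**What the plan says.** The main between-arm method is a crosstab: "Outcomes will be evaluated between the 2 groups using crosstab analysis of the data for the following data". The list that follows covers nightly wet/dry status, compliance, cure, partial improvement and no improvement. Section 3.4.3.1 then adds, as it also does in 3.4.1: "Logistic regression analysis may be performed on the incremental wet dry data vs time to achieving dryness". The sentence does not say which quantity is the outcome, which is the predictor, or where treatment arm enters.

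Follow-up is fixed by section 5.1.1: "Each patient will be in the study for 90 days". Time to dryness does not appear among the outcomes in section 5.2. The only cure definition there is a yes/no item with no time attached: "Is the patient considered cured (dry 29/30 nights) : yes or no". Section 2.1.1 uses a different one when describing the GoGoband device: "Once this stage is completed and the child remains dry for a week consecutively, they are deemed cured".

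Section 3.4.5 gives two drop-out rules. For the categorical outcome: "Patients who drop out of the study will be considered failures for purposes of the study with regards to success vs partial or failure analysis". For nightly data: "Dry /wet night rates will be maintained for the overall analysis of overall dry/wet ratios regardless of the patient ceases participation". Neither covers time to dryness, and no censoring rule or survival method is named anywhere in the document.

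**The concern.** A child who has not become dry by day 90 has no observed time to dryness. All that is known is that the time exceeds 90 days. An analyst working from this text would have to choose the event (29 of 30 nights, one dry week, or something else), the time origin, and what to do with children who never reach the event.

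If the model takes time to dryness as a single number per child, the last choice comes down to dropping those children or assigning them an invented time. Dropping them restricts the analysis to children who succeeded, which is decided after randomisation and probably at different rates in the two arms. Any comparison of speed between arms would then no longer rest on the randomised groups. Because the model is optional and undefined, these choices could also be made after the data have been seen.

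**Working it through.** **1. The plan's own figure.** Section 3.4.2 uses 0.5 for SNEA and 0.8 for GoGoband, one-sided 5%, power 0.8, ratio 1. By the unpooled normal formula, n per group = [p1(1−p1) + p2(1−p2)] × (z0.95 + z0.80)² / (p2−p1)² = (0.25 + 0.16) × (1.645 + 0.842)² / 0.09 = 28.16, so 29. The stated 29 reproduces as a per-group number and does not depend on time to dryness.

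**2. How many children would have no value.** Assume that 0.5 and 0.8 are proportions dry by day 90, and take 50 per arm from section 5.3.1 (the synopsis gives a total of 150, section 5.3.1 a total of 100).
- SNEA: 50 × (1 − 0.5) = 25.
- GoGoband: 50 × (1 − 0.8) = 10.
- Together 35 of 100, and 2.5 times as many in the SNEA arm.

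**3. What dropping them would do.** The documents give no time-to-dryness inputs, so this is an illustration with a constant hazard in each arm: λ = −ln(S90)/90, where S90 is the proportion not dry at day 90.
- SNEA: λ = 0.693/90 = 0.00770. GoGoband: λ = 1.609/90 = 0.01788.
- Median with every child kept, ln 2/λ: 90 against 38.8 days, a gap of about 51 days.
- Median among achievers only, the t at which 1 − exp(−λt) is half the proportion dry: SNEA −ln(0.75)/0.00770 = 37.4 days; GoGoband −ln(0.60)/0.01788 = 28.6 days. The gap is about 9 days.
- Mean among achievers only, 1/λ − 90 × S90/(1 − S90): SNEA 129.8 − 90 = 39.8; GoGoband 55.9 − 22.5 = 33.4. The gap is about 6 days.

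Restricting to achievers hides most of the difference, because the slow and never-dry children are the ones removed.

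**4. Whether a method that keeps everyone is feasible.** Under the same assumptions:
- Hazard ratio = ln(0.2)/ln(0.5) = 2.32.
- Expected events = 25 + 40 = 65.
- Schoenfeld events for 80% power, two-sided 5% = 4 × (1.960 + 0.842)² / (ln 2.32)² = 44.2, so 45.
- Power at 65 events: √(65/4) × 0.842 − 1.960 = 1.44, or about 92%.
- A discrete-time logistic hazard model that keeps never-dry children in the risk set had about 94% power in simulation (400 runs, 50 per arm, two-sided 5%).
- The day-90 crosstab has about 89% by the normal approximation.

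**5. Whether step 4 shows a power advantage.** It does not. These are simulations with 1,500 runs, 50 per arm, two-sided 5%, and 50% against 80% dry by day 90. The start days are assumptions.

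| First possible event (SNEA / GoGoband) | Log-rank | Crosstab |
|---|---|---|
| Day 30 / day 30 | 92% | 90% |
| Day 30 / day 40 | 84% | 89% |
| Day 30 / day 50 | 74% | 90% |

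A later start for GoGoband is plausible because section 2.1.1 says the first 7–10 wetting episodes are used to build the child's model. The small log-rank gain can therefore reverse.

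**The case against.** A reader might infer that logistic regression cannot handle children who never become dry. The documents do not support that. The sentence applies the model to the wet/dry records. If nightly status is modelled against time, a never-dry child contributes wet nights and stays in, although repeated nights within a child then need a random effect or GEE. A discrete-time logistic hazard model is itself a standard survival method. No section says that never-dry children are to be dropped, and sections 3.4.3.3 and 3.4.5 lean the other way by counting drop-outs as failures. All of this stands. The problem arises only when time to dryness is used as a child-level value, but the sentence names that quantity as a variable and does not rule out that use.

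A reader might also infer that the primary comparison is compromised. It is not. The model is one that may be performed, time to dryness is not a listed outcome, the sentence does not mention arm, and the crosstab includes every child.

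Nor do the documents say that half the SNEA arm and a fifth of the GoGoband arm will fail to become dry. Section 3.4.2 says only "A proportion of 0.5 was used for the SNEA and an expected outcome of 0.8 for the GoGoband", without saying what the proportions measure; they could be cure, response or dry-night proportions. Finally, a comparison of mean times among achievers has only about 17% power in simulation under the constant-hazard assumption. That is not a figure for the plan's analysis, because the plan proposes no such test.

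**Conclusion.** The point holds as a gap in specification. An optional model listed under the primary analyses uses a quantity that is undefined for any child not dry by day 90, and the plan gives no event, time origin, censoring rule or drop-out rule for it. One natural way of running it, with time to dryness as a child-level value, would force never-dry children out or give them invented times.

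Its size is conditional: about 35 of 100 children, 25 in the SNEA arm and 10 in the GoGoband arm, if 0.5 and 0.8 are proportions dry by day 90 and 50 per arm are enrolled. The distortion shown above also assumes constant hazards. The argument is about validity and pre-specification, not power.

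**What to change.** Replace the sentence in 3.4.1 and 3.4.3.1 with a supportive time-to-event analysis by arm:

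- **Event and origin.** Time runs from randomisation to the night on which a 29-of-30 dry run is completed, matching the cure item in 5.2.1. State the origin explicitly, because section 3.3.1 allows the alarm to be handed over up to a week after visit 1.
- **Children who do not reach the event** stay in the risk set to day 90.
- **Drop-outs** count as not dry to day 90, in line with 3.4.5, with censoring at the last logged night as a sensitivity analysis. Say whether children removed for non-compliance under 3.3.7 follow the same rule.
- **Method.** Kaplan-Meier curves with a log-rank test, or a discrete-time logistic hazard model with arm as a covariate and intervals starting where a 29-of-30 run first becomes possible. If a Cox model is added, check proportional hazards, because GoGoband has an initial training phase.

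Deleting the sentence would also close the gap, at the price of having no pre-specified analysis of speed.

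The cost is a change of wording and a small amount of extra analysis. Nightly wet/dry records are already collected in both arms (sections 5.1 and 3.2.1), so no new data or patients are needed. The crosstab comparison and the sample size stay as they are.
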